3.3. Interventions (See Addendum 1 for therapy schedules)

3.3.1. Arm 1, control group: High-dose loop diuretics

- At the moment of randomization the patient receives an intravenous bolus of loop diuretics at a dose equal to the double of his normal daily oral dose (e.g. a patient who takes 1x1 mg bumetanide will receive 2x1x1 mg = 2mg; or a patient who takes 2x1 mg bumetanide will receive 2x2x1 mg = 4mg).
- The next three days, the patient will receive the same dose equally divided between two administrations at 10u00 and 16u00 provided that the treating physician has concluded during the morning rounds that the patient is still volume overloaded.
- If diuresis since administration of the previous dose of loop diuretics is <1,500 mL and the patient is still volume overload, subsequent bolus doses are doubled.
- If after doubling of the dose, the patient is considered therapy-refractory. The treating physician is recommended to add chlorthalidone 50mg once daily and consider ultrafiltration or renal replacement therapy after which results of the patient will be censored.
- Switch to treatment at the discretion of the treating physician if any of the following criteria is fulfilled
 - After 3 days
 - The patient had no longer clinical signs or symptoms of congestion
 - Doubling of the serum creatinine value

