3.4. Collected data

- Baseline at the moment of randomization
 - Demographics, medical history, current medical therapy, baseline body weight, blood pressure, heart rhythm (sinus or not), heart rate, Visual-analogue scale (VAS) score for dyspnea and 4-point Likert scale for edema will be assessed upon study inclusion
 - Blood sample: hematocrit, electrolytes, serum osmolality, serum urea, serum creatinine, serum Cystatin C, serum urate, plasma renin activity (PRA), plasma aldosterone, plasma adrenaline, plasma noradrenaline, total protein, plasma NT-proBNP
- Day 1-3:
 - VAS score for dyspnea
 - 4-point Likert scale for edema
 - Body weight and fluid balance
 - Blood pressure, heart rate, heart rhythm
 - Blood sample: hematocrit, electrolytes, serum osmolality, serum urea, serum creatinine, serum Cystatin C, serum urate, PRA, plasma aldosterone, plasma adrenaline, plasma noradrenaline, total protein, plasma NT-proBNP
- Three consecutive 24h urinary collections will be performed; the first one started with the first bolus administration of loop diuretics; urinary assessment of creatinine, protein, sodium, potassium, chloride, ureum, urate, microalbuminuria
- At an outpatient follow-up appointment 2-6 weeks after hospital discharge, a final blood sample with hematocrit, electrolytes, serum osmolality serum urea, serum creatinine, serum Cystatin C, serum urate and plasma NT-proBNP will be collected.
- All-cause mortality and hospital readmissions will be collected prospectively for the study cohort. The patient will receive a telephone call from a study nurse after 3, 6, 9 and 12 months

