3.5. Study end-points

3.5.1. Primary study end-point acetazolamide arm

Total urinary sodium excretion (mmol) after 24 h

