3.5.3. Secondary end-points

- Relative plasma NT-proBNP change (%) after 72 h compared to admission
- Worsening renal function defined as a >0.3 mg/dL increase in serum creatinine or a >20% decrease in estimated glomerular filtration rate by the CKD-EPI formula compared to baseline at any time point before 72 h
- Persistent renal impairment, defined as persistently elevated serum creatinine levels >0.3 mg/dL or a >20% decrease in estimated glomerular filtration rate by the CKD-EPI formula compared to baseline at the moment of outpatient follow-up 2-6 weeks after hospital discharge.
- Peak plasma aldosterone concentration (ng/L) after 72 h
- Peak plasma renin activity (ng/mL/h) after 72 h

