3.5.4. Other pre-specified outcome measures

- Total urinary sodium excretion (mmol) after 48 h and 72 h
- Total urine output after 24 h, 48 h and 72 h
- Change in VAS score for dyspnea at 24 h, 48 h and 72 h
- Change in 4-point Likert scale for edema at 24 h, 48 h and 72 h
- Body weight change upon hospital discharge compared to admission
- Incidence of therapy-refractory congestion defined as the need for combinational diuretic therapy with chlorthalidone, bail-out ultrafiltration or renal replacement therapy

- Incidence of all-cause mortality and readmissions after 1 year

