3.6. Statistical analysis

Continuous variables will be expressed as mean \pm standard deviation when normally distributed and as median (interquartile range) in case of a non-normal distribution. Normality will be assessed by the Shapiro-Wilk statistic. The independent-samples Student's *t*-test and Mann-Whitney *U* test will be used as indicated to compare between groups. Categorical variables will be expressed as percentages and compared using Fisher's exact test or Pearson's χ^2 -test in case of a non-binary response. Statistical significance will always be set at a 2-tailed probability level of <0.05 . All statistics will be performed using IBM SPSS® (Chicago, Illinois, USA) (version 22.0 for Mac).

4. Potential adverse events

- Metabolic acidosis is the only agent-specific adverse event that might be expected from treatment with acetazolamide. Serum bicarbonate is monitored daily. If serum bicarbonate <22 meq/L, substitution with oral NaHCO_3 will be provided.
- Hyperkalemia might be expected as a potential adverse event of spironolactone, but this medication will be withheld when serum potassium levels are >5.0 mmol/L and serum potassium levels are monitored daily throughout the study.

5. References

- american heart association. *Circulation*. 2013;127:e6-e245
2. Effect of enalapril on survival in patients with reduced left ventricular ejection fractions and congestive heart failure. The solvd investigators. *The New England journal of medicine*. 1991;325:293-302

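### Results are censored after rescue for poor diuresis, with no rule for counting those patients, so the 48 h and 72 h outcomes, including the spironolactone primary, lose data depending on response

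*Combined protocol and SAP*

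**What the plan says.** Sections 3.3.1 and 3.3.2 use the same escalation wording for both acetazolamide-arm groups. A patient who passes less than 1,500 mL since the previous loop diuretic dose and is still overloaded moves to the higher dose. After that step a patient may be called therapy-refractory. Chlorthalidone is then recommended, and the physician is to "consider ultrafiltration or renal replacement therapy after which results of the patient will be censored".

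Collection does not depend on rescue. Section 3.4 states: "Three consecutive 24h urinary collections will be performed; the first one started with the first bolus administration of loop diuretics". Blood is also taken on days 1 to 3.

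Outcomes that reach past 24 h:
- Section 3.5.2, the spironolactone primary: hypo- or hyperkalemia over the whole 72 h.
- Section 3.5.3: "Relative plasma NT-proBNP change (%) after 72 h compared to admission"; worsening renal function, judged "compared to baseline at any time point before 72 h"; and peak aldosterone and renin activity.
- Section 3.5.4: "Total urinary sodium excretion (mmol) after 48 h and 72 h", and urine output at the same times.

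The acetazolamide primary (3.5.1) is "Total urinary sodium excretion (mmol) after 24 h". Rescue is an outcome in its own right in 3.5.4: "Incidence of therapy-refractory congestion defined as the need for combinational diuretic therapy with chlorthalidone", with bail-out ultrafiltration and renal replacement also counted.

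Section 3.6 says of the t-test and the Mann-Whitney "test will be used as indicated to compare between groups", and adds Fisher and chi-square tests. It defines no analysis population, no missing-data rule and no method for censored values.

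**The concern.** Rescue follows low urine output, and urine and sodium output are what the 48 h and 72 h comparisons measure. Removing results after rescue therefore selects patients, or parts of their data, on the outcome itself. None of the planned tests can use a censored total, so someone must later decide whether to drop the patient, truncate the total or rank it. That decision could be made with the data in view.

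The starting point of censoring is also unclear. It may begin at chlorthalidone, or only at ultrafiltration or renal replacement. The first reading censors more patients.

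The reach is wider than the acetazolamide comparison. The design is a 2x2 factorial (3.1), so every patient is in both comparisons. The clause censors the patient's results, not one arm's, so potassium events after rescue would be lost from the spironolactone primary.

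**Working it through.** **1. Which outcomes can lose data.** Let the first bolus be given at clock hour t on day 0. With checks on morning rounds at about 10:00, the first check (possible dose increase) is on day 1 and the check after the increase is on day 2. The earliest refractory call is then (24 - t) + 24 + 10 = 58 - t hours after the bolus.
- For t from 08:00 to 20:00 (assumed) this is 50 to 38 h.
- It exceeds 34 h for any t, so the 24 h collection is complete.
- It falls before 48 h whenever t is later than 10:00, and always before 72 h.
- Exception: controls also receive a dose at 16:00. If output were judged then too, the earliest call would be (24 - t) + 16 = 40 - t hours. That is under 24 h for t later than 16:00, for example 20 h at t = 20:00.

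**2. Size if rescued patients are dropped.** The plan gives four groups of 20, so Arm 1 compares 2 x 20 = 40 with 40. It states no power, SD, effect size or rescue rate, so there is no figure to reproduce. Every input below is an assumption: SD 1,000 mL/24 h, day-to-day correlation 0.6, 25% more output after doubling, all patients still overloaded, urine sodium 90 mmol/L (log-SD 0.25), one common 24 h check window, and a 15% benefit. Simulation of 40 v 40 with 8,000 replicates, 72 h sodium:

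| Mean mL/24 h | Share of refractory patients censored | Effect, SD (full data → dropped) | Shrinkage |
|---|---|---|---|
| 2,500 | 20% | 0.316 → 0.305 | 3.6% |
| 2,500 | 50% | 0.316 → 0.286 | 9.4% |
| 2,500 | 100% | 0.316 → 0.253 | 20.1% |
| 3,000 | 20% | 0.357 → 0.352 | 1.6% |
| 3,000 | 50% | 0.357 → 0.343 | 4.1% |
| 3,000 | 100% | 0.357 → 0.328 | 8.3% |

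Shrinkage is 1 - (dropped / full), for example 1 - 0.253/0.316 = 0.20 (percentages come from unrounded effects). At mean 2,500, totals lost are 1.8% of controls v 0.8% of acetazolamide patients if 20% are censored, and 9.1% v 4.0% if all are. Power falls from 28.7% to 26.7% and 19.6% respectively. If doubling does nothing and all are censored, shrinkage at mean 2,500 reaches 25.3%.

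**3. The form of the benefit matters.** The table corresponds to a benefit that adds about the same volume for every patient. A second simulation of the same inputs, with all refractory patients censored at mean 2,500, gives 14.6% for an additive benefit but 0.7% for a proportional one, in which poor responders gain less. Across means 2,500-3,000 the proportional figure is 0.1-0.7%, or at most 2.4% if doubling does nothing. A simpler version with one check at 48 h gives 3.5-13% (additive) and 0.6-2% (proportional). These are effects in SD units. Dropping low-output patients also narrows the SD, so the difference in mmol shrinks somewhat more.

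**4. If totals are truncated at rescue instead.** The effect rises by 0.2-2.8% with an additive benefit and falls by 0.1-1.4% with a proportional one.

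**5. Dependence on the rescue rate.** If a fraction p with the poorest response is dropped, a group's mean rises by ρ·φ(z_p)/(1 - p) SD, where ρ is the correlation between response and outcome. With ρ = 0.8 the rise is 0.156 SD at p = 10% and 0.280 SD at 20%. Equal rates cancel. Rates of 10% (acetazolamide) and 20% (control) give 0.156 - 0.280 = -0.124 SD. A benefit of 0.626 SD, which 40 v 40 detects with 80% power (2.80 × √(2/40)), shrinks to 0.54-0.59 SD at 10% control rescue and to 0.45-0.55 SD at 30% (ρ from 0.8 to 0.5).

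**The case against.** The strongest reply is that little is at stake. The 24 h sodium primary is complete on morning-round checks, and the later sodium and urine totals rank below the secondary end-points. The censoring clause sits directly after ultrafiltration and renal replacement, which need only be considered. On that reading the 20% rows are nearest: at most 1.8% of 40 controls (0.018 × 40 = 0.7 of a patient). The simulation also keeps every patient overloaded, whereas the protocol ends the schedule on decongestion. Setting post-rescue values aside can be legitimate in a mechanistic natriuresis trial, and rescue is counted as an outcome.

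Most of this stands, and it limits the size. It does not supply the missing rule. Counting rescue does not say how the patient enters the other comparisons, and the spironolactone primary is not a minor outcome.

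A reader might infer more than the documents support:
- **That rescued patients are deleted outright.** Deletion is the natural result of the planned tests, but the text does not say so. Keeping urine collected before rescue fits it equally well.
- **That the rule works against acetazolamide.** This needs deletion, an additive benefit and more rescue in controls. Sections 3.3.1, 3.3.2 and 3.6 establish none of these.
- **That it creates false positives.** With no true effect and a common check window, the simulated bias is 0.00 SD and type I error 4.7-4.9%. Error rates of 0.10-0.19 appear only if rescue rates are assumed to differ (20% v 5%, or 30% v 10%) while the outcome does not.
- **That different dosing times make the 1,500 mL trigger unequal.** That depends on Addendum 1, which is cited but is not in the text available here, and on how the blinded schedule is run.

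**Conclusion.** The point holds and should be fixed. The plan prescribes response-dependent loss of results in both acetazolamide-arm groups and names no analysis that can handle it. The 48 h and 72 h sodium and urine totals, the 72 h NT-proBNP change, worsening renal function, the hormone peaks and the spironolactone primary are exposed. The 24 h sodium primary is largely spared, provided refractory status is judged on morning rounds.

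Size and direction are not established. Under the assumed means of 2,500-3,000 mL/24 h and a 15% benefit, dropping rescued patients shrinks the 72 h sodium effect by between near 0% (proportional benefit, or few censored) and about 20% (additive benefit, all refractory patients censored). Truncation moves it by up to about 3% in either direction. Larger losses need stronger assumptions, such as no response to doubling or a 30% rescue rate. The effect on the spironolactone primary was not quantified. The defect rests on the text; the figures show only how much could depend on an unwritten choice.

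**What to change.** In 3.3.1 and 3.3.2, delete the closing clause that censors the patient's results. In 3.6, state that:
- all randomised patients are analysed in their allocated group, for both factorial comparisons, on the scheduled 24 h collections and daily bloods to 72 h, including after chlorthalidone;
- events before rescue (worsening renal function, hypo- or hyperkalemia, hormone peaks) are always counted;
- where ultrafiltration or renal replacement makes a 48 h or 72 h urine total or a 72 h NT-proBNP value missing or uninterpretable, that value gets the worst rank in a Mann-Whitney test. This applies to such values only, not to every patient called refractory.

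An analysis that sets post-rescue values aside may be kept as a sensitivity analysis, with its starting point (chlorthalidone, or only ultrafiltration or renal replacement) stated. Keep the 3.5.4 outcome as it is. One further line should say how creatinine and potassium measured during renal replacement count for a patient with no earlier event.

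The cost is wording, since the samples are already scheduled. The downside is that some values will include the rescue effect, and worst ranks lose the size of the deficit. In the simulation with mean 2,500 and every refractory patient rescued, this costs little. Power is 28.2% when post-rescue values are kept (output assumed 30% higher after rescue) and 28.4% when 20% of rescued patients get the worst rank. That compares with 28.7% on full data and 19.6% with rescued patients dropped. Type I error with worst ranks is 4.7%.

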3.3.2. Arm 1, treatment group: Acetazolamide + low-dose loop diuretics

- At the moment of randomization, the patient receives 500 mg of intravenous acetazolamide and 2 mg of intravenous bumetanide in bolus.
- The next three days, the patient will receive 250 mg of intravenous acetazolamide and 1 mg of intravenous bumetanide in bolus at 10u00 provided that the treating physician has concluded during the morning rounds that the patient is still volume overloaded.

- If diuresis since administration of the previous dose of loop diuretics is <1,500 mL and the patient is still volume overloaded, the patient continues to receive 500 mg of acetazolamide and 2 mg of bumetanide.
- If after doubling of the dose, the patient is considered therapy-refractory. The treating physician is recommended to add chlorthalidone 50mg once daily and consider ultrafiltration or renal replacement therapy after which results of the patient will be censored.
- Switch to treatment at the discretion of the treating physician if any of the following criteria is fulfilled
 - After 3 days
 - The patient had no longer clinical signs or symptoms of congestion
 - Doubling of the serum creatinine value

3.3.3. Arm 2, control group: Discharge spironolactone

This group will receive no active treatment. No placebo will be provided either due to logistic constraints. As instructed by the guidelines, addition of a MRA to maintenance therapy will be recommended upon discharge from the hospital.

3.3.4. Arm 2, treatment group: Upfront spironolactone

This group will receive oral spironolactone 25 mg immediately after randomization and subsequently each day in the morning (10u00) provided serum potassium levels are <5.0 mmol/L. If no contraindications emerge during hospitalization, spironolactone will be added to the maintenance therapy of the patient upon hospital discharge.

3.3.5. All groups

All groups will receive the same maintenance intravenous therapy with 500 mL Glucose 5% and 3g MgSO₄ administered over a 24en-in-angiotensin system blockers and β-blockers) will be continued at the discretion of the treating physician, but they are recommended to keep maintenance dosages unchanged.

3.4. Collected data

- Baseline at the moment of randomization
 - Demographics, medical history, current medical therapy, baseline body weight, blood pressure, heart rhythm (sinus or not), heart rate, Visual-analogue scale (VAS) score for dyspnea and 4-point Likert scale for edema will be assessed upon study inclusion
 - Blood sample: hematocrit, electrolytes, serum osmolality, serum urea, serum creatinine, serum Cystatin C, serum urate, plasma renin activity (PRA), plasma aldosterone, plasma adrenaline, plasma noradrenaline, total protein, plasma NT-proBNP
- Day 1-3:
 - VAS score for dyspnea
 - 4-point Likert scale for edema
 - Body weight and fluid balance
 - Blood pressure, heart rate, heart rhythm
 - Blood sample: hematocrit, electrolytes, serum osmolality, serum urea, serum creatinine, serum Cystatin C, serum urate, PRA, plasma aldosterone, plasma adrenaline, plasma noradrenaline, total protein, plasma NT-proBNP
- Three consecutive 24h urinary collections will be performed; the first one started with the first bolus administration of loop diuretics; urinary assessment of creatinine, protein, sodium, potassium, chloride, ureum, urate, microalbuminuria
- At an outpatient follow-up appointment 2-6 weeks after hospital discharge, a final blood sample with hematocrit, electrolytes, serum osmolality serum urea, serum creatinine, serum Cystatin C, serum urate and plasma NT-proBNP will be collected.
- All-cause mortality and hospital readmissions will be collected prospectively for the study cohort. The patient will receive a telephone call from a study nurse after 3, 6, 9 and 12 months

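### Planned drug exposure inside the primary 24 h sodium window depends on the hour of the first bolus, and the analysis does not adjust for it

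*Combined protocol and SAP*

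**What the plan says.** Section 3.5.1 makes total urinary sodium excretion at 24 h the primary end-point of the acetazolamide comparison. Section 3.4 sets the clock for it, with three 24 h collections in a row, "the first one started with the first bolus administration of loop diuretics".

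The first bolus is tied to randomization. In the control group (section 3.3.1) it is intravenous loop diuretic at twice what the patient usually takes by mouth in a day. In the acetazolamide group (section 3.3.2), 500 mg acetazolamide and 2 mg bumetanide are given at the same moment.

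Later doses are tied to the ward clock. Control: "The next three days, the patient will receive the same dose equally divided between two administrations at 10u00 and 16u00". Acetazolamide group, over the same three days: "250 mg of intravenous acetazolamide and 1 mg of intravenous bumetanide in bolus at 10u00". In both groups each later day's treatment requires that the physician still finds volume overload at morning rounds.

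Sections 3.1 and 3.2 recruit consecutive patients diagnosed within the previous 8 h and restrict no entry hours. Allocation is in blocks of 4, with no stratification by hour stated. Section 3.6 compares groups by an unadjusted t-test or Mann-Whitney test.

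Blood samples are listed in section 3.4 under Day 1-3 without a clock or elapsed hour. One secondary end-point is "Relative plasma NT-proBNP change (%) after 72 h compared to admission".

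**The concern.** The urine window floats with the patient's arrival and the later doses do not. Two patients in the same group, both still overloaded, can have different amounts of drug scheduled inside the window that defines the primary end-point, only because one was randomized at 08u00 and the other at 20u00. Control has two clock times a day and the acetazolamide group one, so the spread is not the same in both groups.

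Three things are at stake. The 24 h sodium result mixes the effect of a single bolus with that of a bolus plus next-day doses, in proportions set by admission hours. The extra spread in exposure adds outcome variance that the planned tests do not remove. And with 40 v 40, entry hours may differ between groups by chance, with no planned adjustment.

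**Working it through.** The plan states no cumulative exposure per window and no power calculation, effect size or SD, so there is no figure of its own to reproduce beyond the bolus examples in section 3.3.1. Those agree with a first dose of 2D: 1 mg a day gives 2 mg, and 2 mg a day gives 4 mg.

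**Inputs (sections 3.3.1, 3.3.2 and 3.4).** D is the daily oral loop dose in mg bumetanide equivalent. Control: 2D at time t, then D at 10u00 and D at 16u00 on each of three days. Acetazolamide group: 2 mg bumetanide + 500 mg acetazolamide at t, then 1 mg + 250 mg at 10u00 on each of three days.

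**Assumptions.** The three days are the calendar days after the day of randomization, overload persists, and doses are not escalated.

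**Formulas for a window of W hours from t.** Control = 2D + D × Nc, where Nc counts the 10u00 and 16u00 times inside the window. Acetazolamide group = 2 + Na mg bumetanide and 500 + 250 × Na mg acetazolamide, where Na counts the 10u00 times.

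| Entry | Nc, Na (24 h) | Control, 24 h | Acetazolamide group, 24 h | Control, 72 h | Acetazolamide group, 72 h |
|---|---|---|---|---|---|
| before 10u00 | 0, 0 | 2D | 2 mg + 500 mg | 6D | 4 mg + 1,000 mg |
| 10u00 to 16u00 | 1, 1 | 3D | 3 mg + 750 mg | 7D | 5 mg + 1,250 mg |
| after 16u00 | 2, 1 | 4D | 3 mg + 750 mg | 8D | 5 mg + 1,250 mg |

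**Spread by hour, 24 h.** Control 4D / 2D = 2.0-fold; acetazolamide group 3 / 2 = 1.5-fold. Over 72 h the spread narrows to 8D / 6D = 1.33 and 5 / 4 = 1.25.

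**Ratio of loop doses, control to acetazolamide group, 24 h.** For D = 1: 2/2 = 1.00, 3/3 = 1.00, 4/3 = 1.33. For D = 2: 4/2 = 2.00, 6/3 = 2.00, 8/3 = 2.67. The ratio is the same in the first two bands and rises by a third only for entry after 16u00.

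**Time left to act.** For entry at clock hour t after 10u00, the next day's 10u00 dose has t − 10 hours left in the 24 h window; for entry after 16u00, the 16u00 dose has t − 16. Entry at 12u00 leaves 2 h. Entry at 20u00 leaves 10 h and 4 h.

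**After midnight.** For a bolus at 02u00 with D = 1, the 24 h control dose is 2 mg if later dosing starts the next calendar day, but 2 + 1 + 1 = 4 mg if it starts that same morning (acetazolamide group 2 v 3 mg). The text does not say which.

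**Escalation.** Section 3.3.1 doubles later boluses when urine output since the last dose is under 1,500 mL and overload persists; section 3.3.2 then keeps the starting doses. If this applied from the first later dose, the 24 h totals would be 2D / 4D / 6D in control and 2 / 4 / 4 mg in the acetazolamide group.

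**Chance imbalance (entry shares assumed).** If a fraction p enters after 16u00, the difference in counts between two groups of 40 has SD √(2 × 40 × p(1 − p)). For p = 0.5 this is √20 = 4.47, and a gap of 6 or more patients has probability about 0.22. For p = 0.25 it is √15 = 3.87, with probability about 0.15.

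**Precision (variance shares assumed).** Take a difference of 0.63 SD, which 40 v 40 detects with 80% power at two-sided 0.05. If hour-driven exposure makes up a share f of the outcome variance, the SD grows by 1/√(1 − f). Power becomes 78%, 76% or 71% for f = 5%, 10% or 20%. The documents do not say which f applies.

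**The case against.** Entry hour is fixed before randomization and balanced in expectation, so the unadjusted test is valid. Starting the collection at the first bolus agrees with the 24 h end-point, and the trial can be read as comparing two strategies under ordinary ward dosing times. This stands: a reader might infer systematic bias against one group, and the documents do not support that.

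Nominal doses also overstate the swing. Later doses depend on persisting overload, and a dose with 2 h left in the window is counted in full. This stands too: the sums describe the schedule, not effective exposure. A reader might also infer that the loop-dose ratio shifts in every band; in the 24 h window it shifts only after 16u00.

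Section 3.3 refers to Addendum 1 for therapy schedules. It is not in the supplied text and may define the days or hours. That could settle the calendar reading, but section 3.6 would still contain no adjustment.

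A further tempting reading is that the 72 h biomarkers are drawn many hours early in evening patients. That needs an assumed morning draw, which section 3.4 does not state. The same Day 1-3 list holds the dyspnea and edema scores, which section 3.5.4 places at 24, 48 and 72 h, suggesting that the days may already mean elapsed hours. Potassium is an incidence over the 72 h interval that also counts supplementation, and aldosterone and renin are peak values. Only NT-proBNP is a single 72 h reading among these.

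**Conclusion.** The point holds as a matter of efficiency and interpretation. On the calendar-day reading, with persisting overload and no escalation, planned loop diuretic in the primary window varies 2.0-fold by entry hour in control and 1.5-fold in the acetazolamide group, and the ratio between groups rises by a third for entry after 16u00. The consequence is avoidable variance, exposure to chance imbalance at 40 v 40, and a treatment contrast that depends on the mix of entry hours. The documents give neither an SD nor a distribution of entry hours, so the loss of power can only be illustrated.

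On blood samples, what remains is that Day 1-3 should be stated in elapsed hours, mainly for NT-proBNP.

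**What to change.** 1. Replace the unadjusted comparison of 24 h sodium in section 3.6 with a linear model containing treatment and the time band of the first bolus (before 10u00, 10u00 to 16u00, after 16u00). Use the same model for 48 h and 72 h sodium and for urine output.
2. Report treatment effects by band as a descriptive sensitivity analysis. The covariate removes variance and chance imbalance but does not show whether the contrast differs by hour.
3. Tabulate loop diuretic and acetazolamide actually given in 0-24 h and 0-72 h, by group and band, beside the primary result.
4. State Day 1-3 in elapsed hours.
5. Reconcile the fixed-clock dose schedule with the floating windows, including what the following days mean for a bolus after midnight.

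Items 1 to 4 change no dose. The cost is two degrees of freedom, one extra table, and recording the times of the first bolus and later doses. The band estimates will be imprecise at this sample size and should be presented as such.
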